4.3.2 Protocol Deviations

Major protocol deviations and any action to be taken regarding the exclusion of subjects or affected data from PK set are defined in the project-specific Protocol Deviation Specification.

- A summary of the number and percentage of subjects with a major protocol deviation by type of deviation will be provided for Enrolled set.
- A summary of the number and percentage of subjects excluded from PK set by type of reason will be provided for Enrolled set.
- A by-subject listing of protocol deviations will be provided.

4.4 Analysis Populations

4.4.1 Definitions

A subject will be defined as screened after the signature of the informed consent, regardless of the completion of all the screening procedures.

A subject will be defined as eligible if he/she meets all the inclusion/exclusion criteria. Otherwise he/she will be defined as a screen failure.

A subject will be defined as enrolled in the study if he/she is included into the interventional phase of the study.

The following analysis sets are defined:

- Enrolled set: all enrolled subjects. This analysis set will be used for demographic, baseline and background characteristics
- Safety set: all subjects who receive at least one dose of IMP. This analysis set will be used for the safety analyses
- PK set: all enrolled subjects who fulfil the study protocol requirements in terms of IMP intake and have evaluable PK data readouts for the planned analyses, with no major deviations that may affect the PK results. This analysis set will be used for the statistical analysis of the PK parameters.

Each subject will be coded as valid or not valid for the safety and the PK set. Subjects will be evaluated according to the treatment they actually receive.

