8 CLINICAL SUPPLIES

8.1 Treatment

All the subjects enrolled in the study will receive the same treatment with the investigational medicinal product (IMP), i.e. NAC, 300 mg/ 3 mL solution for injection, as follows:

- on day 1 at 08:00 ±1 h, one dose of 600 mg of NAC (300 + 300 mg ampoule) will be administered under fasting conditions;

After a wash-out of 3 days:

- on days 4 and 5 at 08:00 ±1 h and 20:00 ±1 h and at 08:00 ±1 on day 6, 5 doses of 600 mg of NAC (300 + 300 mg ampoule) will be administered.

8.1.1 *Description of products*

8.1.1.1 *Test product*

IMP	NAC 300 mg/ 3 mL solution for injection
Active substance	N-acetyl-L-cysteine
Manufacturer (active substance)	F.I.S. Fabbrica Italiana Sintetici S.p.A., [name] (GMP compliant)
Manufacturer (finished product)	Zambon S.p.A., [name] (GMP compliant)
Pharmaceutical form	Solution for injection
Dose	300 mg/ 3 mL
Administration route	Parenteral

The analytical certificates will be supplied with the IMP. Quali-quantitative formulation is as follows:

Each 3 mL vial (10%) contains:

- N-acetyl-L-cysteine (NAC) 300 mg
- sodium hydroxide 74 mg
- disodium edetate 3 mg
- water for injections q.s. to 3 mL

8.1.2 *Dose regimen*

Two ampoules of IMP (300 + 300 mg) corresponding to a total dose of 600 mg of NAC diluted in 10 mL of NaCl 0.9% sterile saline solution, will be administered by a 5-minute i.v. infusion.

Single dose:

One (1) dose of IMP will be administered under fasting conditions on day 1 at 08:00 ±1 h.

Multiple dose regime:

Five (5) doses of IMP will be administered twice a day (b.i.d.) on days 4 and 5 at 08:00 ±1 h and 20:00 ±1 h and one dose will be administered on day 6 at 08:00 ±1.

8.1.3 *Route and method of administration*

Each dose of IMP will be prepared by diluting the content of 2 ampoules of IMP in 10 mL of saline, as described above (§ 8.1.2), and administered to each study subject at the clinical site only by the investigator or his/her deputy.

Each dose will be infused intravenously over 5 min.

The start of infusion (not the end) will be considered as time 0.

8.1.4 *Investigational product distribution*

The IMP will be exclusively used for the present clinical study and will only be administered to the subjects enrolled in the study.

8.2 *Packaging and labelling*

The IMP primary packaging will be glass vials.

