3.2 Pharmacokinetics and Safety Variables

3.2.1 Pharmacokinetics Variables

The derivation of PK parameters will be the responsibility of Quantitative Clinical Development (QCD), PAREXEL International. PK parameters will be calculated by non-compartmental analysis methods following these guidelines;

- Actual sampling times relative to dosing rather than nominal times will be used in the calculation of all derived PK parameters.
- There will be no imputation of missing data.
- Any subjects with missing concentration data will be included in the analysis provided that at least C_{max} and $AUC_{(0-t)}$ can be reliably calculated

The following PK parameters will be measured and/or calculated for plasma and urine NAC data, using the validated software Phoenix® WinNonlin® version 8.0 or higher (Certara USA, Inc., Princeton, NJ) (actual version will be stated in the final report), after a single dose of the Investigational Medicinal Product (IMP):

C_{max} :	Maximum NAC plasma concentration will be obtained directly from the concentration data
t_{max} :	Time to achieve C_{max}
k_{el} :	Terminal elimination rate constant, calculated, by linear regression s 
- Only those data points that are judged to describe the terminal log-linear decline will be used in the regression.- A minimum number of three data points in the terminal phase will be used in calculating Kel with the line of regression starting at any post-C_{max} data point (C_{max} should not be part of the regression slope) and including C_{last}, t_{last}.- The correlation coefficient (R^2) in general should be greater than 0.80.
$t_{1/2}$:	Half-life, calculated, if feasible, as $\ln 2/k_{el}$
$AUC_{(0-t)}$:	Area under the concentration-time curve from single dose to the last observed concentration time t , calculated with the linear up/log down trapezoidal method
$AUC_{(0-\infty)}$:	Area under the concentration-time curve extrapolated to infinity, calculated, if feasible, as $AUC_{(0-t)} + C_t/k_{el}$, where C_t is the last measurable drug concentration
$AUC_{(0-12)}$:	Area under the concentration-time curve from single dose to 12 h post-dose, calculated with the linear up/log down trapezoidal method

%AUC _{extra} :	Percentage of the AUC _(0-∞) obtained by extrapolation, calculated as; $(1 - [\text{AUC}_{(0-t)} / \text{AUC}_{(0-∞)}]) \times 100$
V _d :	Volume of distribution associated with the terminal slope, calculated, if feasible, as Dose/(AUC _(0-∞) *k _{el})

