4.4.2 Reasons for exclusion from the PK set before statistical analysis

Reasons for the exclusion of subjects from the PK set are the following:

- intake of concomitant medications which could render the plasma concentration-time profile unreliable
- Adverse events (AEs) which could render the plasma concentration-time profile unreliable
- administration errors which could render the plasma concentration-time profile unreliable
- other events which could render the plasma concentration-time profile unreliable

If one of these events occurs, it will be noted in the Case report form (CRF) during the study.

The samples from the subjects excluded from the PK set should still be assayed and the results listed. Subjects should not be excluded from the PK set if the AUC_{0-t} covers less than 80% of the $AUC_{0-\infty}$.

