4.4.3 Analysis

- A summary of subjects included in each analysis set will be provided for Enrolled Set.
- By-subject listing including analysis set flag (Yes or No), and reason of exclusion from safety and PK set will be provided.

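### Does the single PK-set flag in SAP 4.4.1 remove intact single-dose profiles when dosing on Days 4-6 fails?

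*SAP*

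**What the plan says.** SAP 4.4.1, in the same terms as Protocol v3.0 section 15.1.1, has a single population for the PK analysis, described as "all enrolled subjects who fulfil the study protocol requirements in terms of IMP intake and have evaluable PK data readouts for the planned analyses", provided there is no major deviation affecting the PK results. It adds "Each subject will be coded as valid or not valid for the safety and the PK set", and then that subjects are evaluated by the treatment actually received. SAP 4.4.3 promises this: "By-subject listing including analysis set flag (Yes or No), and reason of exclusion from safety and PK set will be provided". None of these sentences mentions a dosing period.

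The intake in question is one infusion on Day 1 and then, under Protocol v3.0 section 8.1.2, "Five (5) doses of IMP will be administered twice a day (b.i.d.) on days 4 and 5", the fifth of these falling on the morning of Day 6.

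Four other places in the SAP bear on who is analysed:

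- **3.2.1:** "Any subjects with missing concentration data will be included in the analysis provided that at least" two named parameters, Cmax and AUC(0-t), are reliable.
- **4.3.2:** a separate Protocol Deviation Specification defines the action to take "regarding the exclusion of subjects or affected data from PK set".
- **4.4.2:** reasons for exclusion include "administration errors which could render the plasma concentration-time profile unreliable"; it also states "The samples from the subjects excluded from the PK set should still be assayed and the results listed".
- **4.9.3:** outliers may be removed at concentration, parameter or set level. Any excluded subject or outlier is recorded in the data review minutes, with flags at the level of the analysis datasets.

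**The concern.** One Yes/No flag serves two periods that have different data requirements. Protocol v3.0 section 14.1.1 lists 21 primary variables. Twelve are single-dose parameters, whose sampling ends on Day 2. A subject who withdraws or is misdosed on Days 4-6 fails the intake condition if it is read as covering all six infusions, and could then drop out of summaries for which the data are complete.

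Drop-outs are not replaced, so each such exclusion would shrink the single-dose tables. The SAP does not say which of its exclusion rules prevails, so the choice might be made once concentrations are known. If withdrawal were related to exposure, the single-dose summaries could also shift, although nothing in the documents shows such a link.

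**Working it through.** **Can a Day 4-6 event damage the Day 1-2 profile?** The last single-dose sample is at 32 h. The first repeated dose, on Day 4 at 08:00, is nominally 72 h after the Day 1 dose. The gap is 72 − 32 = 40 h, so the single-dose profile is finished before anything can go wrong with the later infusions.

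**What the rules do in the two cases.**

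| Case | Rule that applies | Result for single-dose data |
|---|---|---|
| Subject stops after Day 3 | 3.2.1: missing concentrations tolerated if Cmax and AUC(0-t) are reliable. These are the single-dose names; the multiple-dose ones are Css_max and AUCss(0-t) | Points to keeping them |
| Subject misdosed on Days 4-6 | 4.4.2: exclusion needs an unreliable profile. 4.3.2: subject or affected data, as the Protocol Deviation Specification defines | Day 1-2 profile is reliable, so 4.4.2 gives no reason to drop it; the detailed rule is in a document not available here |

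SAP 4.9.3 reports n for each PK parameter, and SAP 3.2.1 allows individual extrapolated parameters to be reported as not calculated. The tables can therefore already carry a different n from one parameter to the next. The accumulation ratio R needs AUC from both periods, so it is available only for subjects with both.

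**Size if subjects were excluded anyway.** The plan has no figure to reproduce: 24 was chosen without a calculation and no drop-out rate is given. I assume 1 to 4 subjects affected.

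- Profiles lost: 1/24 = 4.2% per subject, up to 4/24 = 16.7%.
- Rise in the standard error of a log mean, √(24/n) − 1, whatever the CV: 2.2% (n=23), 4.4% (n=22), 6.9% (n=21), 9.5% (n=20).
- 95% CI factor of a geometric mean, exp(t(0.975, n−1)·σ/√n), with σ = √ln(1+CV²):

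| CV | Source | n=24 | n=20 |
|---|---|---|---|
| 10.2% | 9.6/93.9, total-NAC AUC, six healthy subjects (Protocol v3.0 Table 6.2.3) | 1.044 | 1.049 |
| 20% | assumed | 1.087 | 1.097 |
| 30% | assumed | 1.132 | 1.147 |
| 50% | assumed | 1.221 | 1.247 |

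This interval is only a yardstick; SAP 4.9.3 does not list it among the descriptive statistics for PK parameters.

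**Would the event occur at all?** If each subject has a 2%, 5% or 10% chance (assumed) of stopping or being misdosed on Days 4-6, the chance of at least one case, 1 − (1−p)^24, is 38%, 71% or 92%. The expected number, 24p, is 0.5, 1.2 or 2.4. Subjects are confined from Day -1 to Day 8, and only the investigator or a deputy gives the infusions. That limits the opportunity for missed or wrong doses but does not exclude it.

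**The case for a change.** The best argument for a change is that no sentence ranks these rules. SAP 3.2.1 deals with missing concentrations, not with failed intake. SAP 4.4.2 speaks of the concentration-time profile without saying which of the two, and excludes the subject rather than the period. The data-level rule is handed to a specification that is not among the documents. The SAP could have been explicit, since its adverse event overview in 4.10.1 is split by single and multiple dose. Outlier exclusions under 4.9.3 are discussed after the concentrations arrive. Two period-specific sets, with R on their overlap, would match what each parameter needs.

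Part of this stands. The order of precedence is unwritten, and for misdosing the available documents cannot settle the matter. But every rule that addresses the situation points to keeping an intact single-dose profile. Only a strict reading of the intake condition points the other way, and the sentence about treatment actually received weakens that reading.

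An unexpected exclusion would also be visible. SAP 4.3.2 summarises exclusions by reason, 4.4.3 lists them by subject, and 4.4.2 keeps the excluded subjects' results in the listings.

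The timing also counts against a change. According to its revision history, SAP 4.0 followed database lock and the sponsor's review of the final outputs. Redefining the set for the primary variables at that stage would itself be a choice made with the data in view. It would also depart from the identical definition in Protocol v3.0 section 15.1.1.

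**Conclusion.** No change to the plan is needed. The observation about the wording is accurate: there is one PK set and one code, with no mention of period. It amounts to missing detail that a pharmacokineticist would fill in the obvious way, by judging evaluability for the profile a parameter comes from and requiring both periods only for R.

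The effect is conditional and small. It is zero if no subject fails on Days 4-6; otherwise it is 1 of 24 single-dose profiles per subject if the strict reading were applied. At the assumed worst of four subjects the standard error rises 9.5%, and the CI factor moves from 1.132 to 1.147 at an assumed CV of 30%. The study is descriptive, with no hypothesis test that this could tip.

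The conclusion rests on two assumptions: that few subjects, if any, are affected, and that the Protocol Deviation Specification follows the affected-data approach announced in SAP 4.3.2.

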4.4.2 Reasons for exclusion from the PK set before statistical analysis

Reasons for the exclusion of subjects from the PK set are the following:

- intake of concomitant medications which could render the plasma concentration-time profile unreliable
- Adverse events (AEs) which could render the plasma concentration-time profile unreliable
- administration errors which could render the plasma concentration-time profile unreliable
- other events which could render the plasma concentration-time profile unreliable

If one of these events occurs, it will be noted in the Case report form (CRF) during the study.

The samples from the subjects excluded from the PK set should still be assayed and the results listed. Subjects should not be excluded from the PK set if the AUC_{0-t} covers less than 80% of the $AUC_{0-\infty}$.

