15.1 Analysis Sets

15.1.1 *Definitions*

A subject will be defined as screened after the signature of the informed consent, regardless of the completion of all the screening procedures.

A subject will be defined as eligible if he/she meets all the inclusion/exclusion criteria. Otherwise he/she will be defined as a screen failure.

A subject will be defined as enrolled in the study if he/she is included into the interventional phase of the study.

The following analysis sets are defined:

- Enrolled set: all enrolled subjects. This analysis set will be used for demographic, baseline and background characteristics
- Safety set: all subjects who receive at least one dose of IMP. This analysis set will be used for the safety analyses
- PK set: all enrolled subjects who fulfil the study protocol requirements in terms of IMP intake and have evaluable PK data readouts for the planned analyses, with no major deviations that may affect the PK results. This analysis set will be used for the statistical analysis of the PK parameters.

Each subject will be coded as valid or not valid for the safety and the PK set. Subjects will be evaluated according to the treatment they actually receive.

15.1.2 *Reasons for exclusion from the PK set before bioanalysis*

Reasons for the exclusion of subjects from the PK set are the following:

- intake of concomitant medications which could render the plasma concentration-time profile unreliable
- AEs which could render the plasma concentration-time profile unreliable
- administration errors which could render the plasma concentration-time profile unreliable
- other events which could render the plasma concentration-time profile unreliable

If one of these events occurs, it will be noted in the CRF during the study.

The samples from the subjects excluded from the PK set should still be assayed and the results listed. Subjects should not be excluded from the PK set if the AUC_{0-t} covers less than 80% of the $AUC_{0-\infty}$.

15.2 *Sample size and power considerations*

The sample size was not calculated through any statistical calculation. A sample size of 24 subjects was estimated as sufficient for the descriptive purposes of the present study. Drop-out subjects will not be replaced.

15.3 *Demographic, baseline and background characteristics*

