1 INTRODUCTION

This SAP is based upon the following study documents:

- Study Protocol, Version 3.0 (Dec 03, 2019)
- electronic Case Report Form (eCRF), Version 3.0 (Oct 14, 2019)

The Statistical Analysis Plan (SAP) details the statistical methodology to be used in analyzing study data and outlines the statistical programming specifications for the Tables, Listings, and Figures. It describes the variables and populations, anticipated data transformations and manipulations and other details of the analyses not provided in the Clinical Study Protocol (CSP).

The SAP will be finalized prior to database lock (DBL) and describes the statistical analysis as it is foreseen when the study is being planned. If circumstances should arise during the study rendering this analysis inappropriate, or if improved methods of analysis should arise, updates to the analyses may be made. Any deviations from the SAP after DBL, reasons for such deviations and all alternative or additional statistical analyses that may be performed, will be described in a SAP Addendum.

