4.9.3 Pharmacokinetic Parameters

Pharmacokinetic parameters will be listed by subject. Descriptive statistics for calculated PK parameters will include: n, arithmetic mean, SD, CV%, geometric mean, geometric CV%, median, minimum and maximum values. For t_{max} , only median, minimum and maximum values will be presented. No descriptive statistics will be determined when fewer than three individual PK parameters are available.

The following rules will be followed with regards to the number of decimal places and presentation of data in the tables and listings for PK parameters:

- Individual PK parameters will be presented to four significant digits, with the exception of t_{max} , which will be presented to two decimal places.
- Parameters derived directly from source data (e.g. C_{max}) shall be reported with the same precision as the source data (if this is not four significant digits).
- The mean, geometric mean, median and SD values will be reported to four significant digits except for CV% which will be presented to one decimal place.
- For t_{max} the minimum and maximum will be presented to two decimal places and all other descriptive statistics will be presented to three decimal places.
- Estimates and confidence intervals in the form of percentages will be presented to two decimal places.

After receiving Plasma and urine PK concentration data from Vendor, statistical outlier testing will be performed by using boxplots to identify outliers as described below:

- Q1: 25th percentiles; Q3: 75th percentiles; Interquartile Range (IQR) = Q3 – Q1;
- Lower Far outlier: value < Q1 – 3 × IQR;
- Upper Far outlier: value < Q3 + 3 × IQR.

The far outliers will be identified, reviewed and discussed during the Data Review Meeting prior to Database lock. Outliers that may have an impact on the concentration-time profiles will be discussed and it will be determined whether to exclude them from PK concentrations, PK parameters or PK set. As a general rule, outliers will be ruled out from tabulations but kept in data listings.

If a subject or outlier is required to be excluded from PK analysis, details will be documented in Data Review Meeting minutes, including an external excel file that documents the required Analysis Flag on applicable analysis datasets level.

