4.12 Changes in the Conduct of the Study or Planned Analysis

Not Applicable.

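### SAP 4.4.2 allows event-based exclusions from the PK set to be decided after concentrations are known, whereas protocol 15.1.2 places them before bioanalysis, and SAP 4.12 declares no change

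*SAP*

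**What the plan says.** Protocol v3.0, section 15.1.2, is headed "Reasons for exclusion from the PK set before bioanalysis". It gives four reasons: concomitant medication, adverse events, administration errors, and a residual category. Each applies if it could make the plasma profile unreliable.

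SAP section 1 states that the SAP is based on protocol v3.0. SAP 4.4.2 carries over the four reasons, including "other events which could render the plasma concentration-time profile unreliable", but its heading reads "Reasons for exclusion from the PK set before statistical analysis". It keeps the sentence on recording: "If one of these events occurs, it will be noted in the Case report form (CRF) during the study". It also keeps the instruction that excluded subjects' samples are assayed and listed all the same, and the bar on excluding a subject because the observed AUC covers less than 80% of the extrapolated AUC.

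SAP 4.9.3 describes what happens once results arrive: "After receiving Plasma and urine PK concentration data from Vendor, statistical outlier testing will be performed by using boxplots". Far outliers are then discussed at a Data Review Meeting before database lock, where they may be removed from concentrations, parameters or the PK set. The section adds: "If a subject or outlier is required to be excluded from PK analysis, details will be documented in Data Review Meeting minutes".

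SAP 4.12, on changes to the planned analysis, says "Not Applicable". The SAP revision history does not mention the changed heading.

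**The concern.** The four reasons ask whether something could have made a profile unreliable. No threshold is set, and the last reason is open-ended. Such criteria are safest when applied from clinical facts alone. If the decision is taken with the profile on the table, a minor recorded event is more likely to be judged disqualifying when the profile looks unusual than when it looks typical.

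The trial is open-label, single-arm and descriptive, so type I error is not at stake. What is at stake is the study's main product: the PK summaries and their between-subject variability, which form part of a registration package for China. Selective removal of extreme subjects shifts the mean and makes variability look smaller than it is.

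**Working it through.** **Step 1. The texts side by side.**

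| Item | Protocol v3.0, 15.1.2 | SAP 4.4.2 |
|---|---|---|
| Timing in the heading | before bioanalysis | before statistical analysis |
| Four reasons | listed | same four |
| Event noted in CRF during the study | yes | yes |
| Excluded subjects still assayed and listed | yes | yes |
| Date, sign-off or data-release rule in the body text | none | none |

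The only difference that matters is the time point in the heading. Protocol v1.0 and v2.0 carry the same heading as v3.0, so the SAP is not following superseded text.

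**Step 2. Does the SAP wording reach past the assay?** A decision before bioanalysis is also before statistical analysis, so the SAP wording does not forbid the protocol's order. It removes the upper limit, however. Under 4.9.3 the concentrations are in hand at the Data Review Meeting, and its minutes are where exclusion of a subject or an outlier is documented. Event-based removal with profiles visible is therefore allowed.

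**Step 3. Size.** The documents give no figure to reproduce: 24 was not derived from a formula, and no variability is assumed for the study. The following is an illustration of the worst single removal.

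Inputs:
- n = 24 (protocol 15.2; SAP 4.11).
- Variability: protocol Table 6.2.3 gives a total-NAC AUC of 93.9 ± 9.6 after 600 mg i.v. in 6 healthy controls, so CV = 9.6/93.9 = 0.102, taken as 10%.
- CVs of 15%, 25% and 35% are assumptions, to show the range.
- AUC is taken as log-normal, with log-scale SD σ = √ln(1 + CV²).

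Formulas:
- The expected maximum of 24 standard normal values is 1.948 (simulated). Dropping it shifts the mean log by −1.948σ/23 = −0.0847σ, so the geometric mean changes by exp(−0.0847σ) − 1.
- The sample log-SD, s, averages 0.989σ with all 24 values and 0.914σ with the lower 23 (simulated). The SAP 4.9.1 formula is gCV = √(exp(s²) − 1).

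At CV 10%, σ = √ln(1.01) = 0.0998:
- geometric mean: exp(−0.00845) − 1 = −0.84%
- gCV: s goes from 0.0987 to 0.0912, so gCV goes from 9.9% to 9.1%

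At CV 25%, σ = √ln(1.0625) = 0.2462:
- geometric mean: exp(−0.02085) − 1 = −2.06%
- gCV: s goes from 0.2435 to 0.2250, so gCV goes from 24.7% to 22.8%

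Simulation of 24 log-normal values gives the same results:

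| CV | Change in geometric mean | gCV, all 24 | gCV, highest removed |
|---|---|---|---|
| 10% (Table 6.2.3) | −0.8% | 9.9% | 9.1% |
| 15% (assumed) | −1.3% | 14.8% | 13.7% |
| 25% (assumed) | −2.1% | 24.7% | 22.8% |
| 35% (assumed) | −2.8% | 34.7% | 31.9% |

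The gCV falls by about 8% of its value throughout (9.1/9.9 = 0.92; 22.8/24.7 = 0.92). Reported variability is affected more than the mean.

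**The case against.** The strongest reply is that only a heading phrase differs and that the SAP is otherwise well guarded. Most of this stands:

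- The triggering event has to be noted in the CRF during the study, which makes it hard to find a reason afterwards.
- Exclusions are summarised by type of reason (SAP 4.3.2) and listed by subject with the reason (SAP 4.4.3). Excluded subjects are still assayed and listed, so a reader could see any removal and reverse it.
- SAP 4.3.2 refers to a Protocol Deviation Specification that is not among the documents and may narrow the discretion.
- The PK set definition in both documents requires evaluable PK data, so the protocol never was wholly pre-assay.

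These points limit the concern without removing it. Listings and minutes make a decision visible; they do not blind it. A recorded event can still be judged disqualifying or harmless in the light of the profile. Assessing evaluability may need assay results, but judging an adverse event or a dosing error does not.

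A reader might infer more than the documents support, in three ways:

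- *That the SAP schedules event-based exclusions after the assay.* It does not. The decision wording in 4.9.3 concerns far outliers, and the sentence on a subject or outlier says where an exclusion is recorded, not when event-based decisions are taken. The instruction to assay excluded subjects' samples even suggests that some are expected to be excluded beforehand.
- *That pre-assay timing is the only protection.* The safeguards above show otherwise.
- *That the protocol contains a signed list or a release gate which the SAP dropped.* It contains neither.

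**Conclusion.** The two documents conflict on when event-based exclusions are decided, and the conflict is undeclared. The SAP permits such removals after concentrations are known; nothing shows that any were planned or made. The effect on the mean is modest: about −0.8% for the worst single removal at the only CV the documents support, and −2.1% at an assumed 25%. Understatement of variability is proportionally larger. The figures assume log-normal AUC and that the one subject removed is always the highest. The 10% CV rests on six subjects in one study, and the protocol itself warns that the i.v. literature is poorly comparable. The point is worth correcting because correction is cheap and these summaries are the primary output, not because a conclusion would be overturned.

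**What to change.** In SAP 4.4.2, restore the protocol's timing for the four event-based reasons. State that these decisions are taken from CRF data and dated before concentrations are released. Keep post-assay judgement for evaluability only, for example a documented sample or assay failure. The dating requirement goes a step beyond the protocol, which sets the time point but no record of it.

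This may now be too late. The revision history describes SAP version 3.1 as written after database lock and review of the final outputs, and version 4.0 followed. If concentrations had been released before the event-based decisions were made, declare the departure in SAP 4.12 or in the addendum that SAP section 1 provides for. Then report the PK summaries with and without any subject excluded after the assay. If no subject was excluded in that way, one sentence saying so settles the matter.

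The cost is a few lines of SAP text and either one dated record or, at most, a second set of PK summary tables. No new data are needed.
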